### TRACE RA-DAS (sub-study only):

EULAR moderate or good response based on DAS 28 at 6 months

### 3.2 Secondary and tertiary endpoints

### **TRACE RA secondary endpoints**

Components of the primary endpoint separately:

Coronary events

Presumed ischaemic stroke or TIA;

Any arterial revascularisation

Cardiovascular death excluding both confirmed cerebral haemorrhage [ICD I64-99 in the 10th International Classification of Diseases]) and non-coronary cardiac death [ICD I00-I15 and I26-I52]

### TRACE RA tertiary endpoints

Total and cause-specific mortality (coronary, other vascular and non-vascular death separately) Hospitalisations for various other causes Statin safety-related outcomes (persistent elevation of ALT or AST; myopathy (defined as muscle symptoms plus CK>10 x upper limit normal) Differences in lipid levels during follow-up in a random sample Functional outcome assessed by HAQ and EQ5D

Allowance for multiple hypothesis testing in these analyses will be made using the "Bonferroni" correction.

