### 3.1 Primary endpoints

### TRACE RA (all patients): Primary endpoints

The primary comparison will involve Cox regression analyses of "major vascular events" (defined as nonfatal myocardial infarction, non-fatal presumed ischaemic stroke, transient ischaemic attack, any coronary or non-coronary revascularisation or cardiovascular death excluding both confirmed cerebral haemorrhage [ICD I64-99 in the 10th International Classification of Diseases]) and non-coronary cardiac death [ICD I00-I15 and I26-I52] during the scheduled treatment period among all those allocated atorvastatin tablets versus all those allocated placebo tablets (i.e. "intention-to-treat" comparisons).

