### 10.7 Interim analyses and its frequency

Interim analyses will be performed when the number of events reaches 25%, 50% and 75% of the total expected events. No formal stopping rule will be set but the DMC will advise the Chairman of the Trial Steering Committee that the trial should be stopped if, in DMC's view, the randomised comparison in the trial has provided both (a) proof beyond reasonable doubt that for all, or for some, types of patients the trial treatment is clearly indicated or clearly contraindicated in terms of a net difference in major morbidity and mortality, and/or (b) evidence that might reasonably be expected to influence the patient management of clinicians aware of the results of any other studies. Safety data will be continuously monitored by the independent DMC.

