## A5.2.4 Stroke (any event that meets the criteria listed below for one of the following 3 categories of stroke):

Ischaemic stroke (one of the following conditions must be met):

Rapid onset of focal neurological deficit lasting  $\geq$ 24 hours or leading to death plus evidence from neuroimaging (CT or MRI) showing cerebral/cerebellar infarction or no abnormality, or post-mortem examination showing cerebral and/or cerebellar infarction.

Rapid onset of global neurologic deficit (e.g. coma) lasting  $\geq$ 24 hours or leading to death plus evidence from neuroimaging showing cerebral/cerebellar infarction, or post-mortem examination showing infarction.

Focal neurologic deficit (mode of onset uncertain) lasting  $\geq$ 24 hours or leading to death plus evidence from neuroimaging showing cerebral/cerebellar infarction, or post-mortem examination showing infarction.

Primary intercerebral and/or cerebellar haemorrhage (one of the following conditions must be met):

Rapid onset of focal neurologic deficit lasting  $\geq$ 24 hours or leading to death plus evidence from neuroimaging or post-mortem examination showing primary intracerebral and/or cerebellar haemorrhage.

Rapid onset of global neurologic deficit (e.g. coma) lasting  $\geq$ 24 hours or leading to death, plus evidence from neuroimaging or post-mortem examination showing primary intracerebral and cerebellar haemorrhage.

Focal neurologic deficit (mode of onset uncertain) lasting  $\geq$ 24 hours or leading to death, plus evidence from neuroimaging or post-mortem examination showing primary intracerebral and/or cerebellar haemorrhage.

Stroke- mechanism unknown (one of the following conditions must be met):

Rapid onset of focal neurologic deficit lasting  $\geq$ 24 hours or leading to death, without neuroimaging or post-mortem data available.

Rapid onset of global neurologic deficit (e.g. coma) lasting  $\geq$ 24 hours or leading to death, without neuroimaging or post-mortem data available.

Focal neurologic deficit (mode of onset uncertain) lasting  $\geq$ 24 hours or leading to death, without neuroimaging or post-mortem data available.

*Note:* The following **conditions will be excluded** from the defined endpoint of stroke as outlined above:

Primary intracerebral haemorrhage

Primary subarachnoid haemorrhage

Subdural or extradural haematoma

Traumatic intracerebral haemorrhage

Neurologic deficit due to major metabolic or haemodynamic disturbance

Venous sinus thrombosis

Cerebral tumour

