#### Definitions of non-cardiovascular revascularisations:

#### Non-cardiac procedures

non coronary arterial surgery/intervention unspecified arterial surgery unspecified non coronary angioplasty +/- stent fem-pop bypass/leg artery bypass popliteal or femoral or iliac aneurysm repair aortic aneurysm repair or stent carotid surgery cerebral artery aneurysm surgery or clipping arterial graft reconstruction/excision (not dialysis access) leg artery angioplasty +/- stent renal artery angioplasty +/- stent carotid angioplasty +/- stent non coronary angiogram angiogram of leg/femoral angiogram renal artery angiogram carotid angiogram or arch aortagram Embolectomy

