# Appendix 11.5: The following changes have been incorporated into Version 5 (dated 6th December 2010) of the protocol

#### Summary of Key Points:

- Trial recruitment has been extended to March 2014 with the last follow-up appointment being in March 2016, or until a sufficient number of events has accrued to provide statistical power whichever is the earlier. Recruitment target amended to more than 4000 patients.
- Number of participating centres increased from 100 to 120
- New Power calculations (based on observed recruitment and number of events) and subsequent increase in required sample size.
- Revision of Endpoints to include non-coronary revascularisations, TIA and exclude angina and haemorrhagic stroke
- Pharmacovigilance procedures amended to exclude reporting of adverse events unless an adverse reaction is deemed to have a reasonable causal relationship with atorvastatin. Procedures also amended to provide further guidance on management of patients with new and significant muscle pains.
- Case Report form and blood tests have been simplified
- Patient Information Leaflet Main trial amended in light of protocol amendment and format designed to make it more visually appealing.
- > Patients' addresses to be collected retrospectively and prospectively
- Co-Sponsor (University Of Manchester) representative amended from [name] to [name]

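### Cerebral aneurysm surgery counts as a primary event although haemorrhagic stroke is excluded, and haemorrhagic stroke has no named comparison of its own

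*Protocol*

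**What the plan says.** **Aim and primary endpoint.** Section 2.2.2 aims at atherosclerotic events, fatal or not. In Section 3.1 the non-fatal part of the composite includes "non-fatal presumed ischaemic stroke, transient ischaemic attack, any coronary or non-coronary revascularisation", and the fatal part is "cardiovascular death excluding both confirmed cerebral haemorrhage" and non-coronary cardiac death. Appendix 11.5 shows that this was a deliberate change: "Revision of Endpoints to include non-coronary revascularisations, TIA and exclude angina and haemorrhagic stroke".

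**Stroke definition.** A5.2.4 describes three categories of stroke. One of them is haemorrhagic and requires "evidence from neuroimaging or post-mortem examination showing primary intracerebral and/or cerebellar haemorrhage". The note that follows excludes intracerebral and subarachnoid haemorrhage from the stroke endpoint.

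**Revascularisation definition.** The Primary Endpoints part of Appendix 5 makes non-coronary revascularisation a component and sends the reader further down for its definition. The list at the end of A5.4, under non-cardiac procedures, includes "cerebral artery aneurysm surgery or clipping".

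**Other outcome lists.** The only stroke item among the secondary endpoints in Section 3.2 is "Presumed ischaemic stroke or TIA". The named tertiary safety outcomes are "Statin safety-related outcomes (persistent elevation of ALT or AST; myopathy", with a CK threshold for the latter. Section 11.2 and Appendix 6 add no stroke outcome.

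**Monitoring.** Section 10.7 asks the DMC to judge whether treatment is clearly indicated or contraindicated "in terms of a net difference in major morbidity and mortality".

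**The concern.** There are two linked problems.

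The first is a contradiction inside the primary endpoint. The exclusion takes bleeding out of the composite, and the procedure list lets part of it back in. The list does not separate surgery after a rupture from elective surgery, and neither kind fits the stated atherosclerotic aim. An endpoint committee that follows Appendix 5 literally would reject a subarachnoid haemorrhage as a stroke and accept the clipping that treats it as a primary event.

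The second is a gap. Once haemorrhagic stroke was removed from the primary endpoint, no other list took it up. It is major vascular morbidity, and the main hazard ratio leaves it out without a named companion result beside it. A reader of the final report, and a DMC weighing net morbidity, would want that result.

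**Working it through.** **1. The exclusion against the procedure list.** Take a patient with a ruptured cerebral aneurysm that is clipped.
- Stroke component: the bleed does not count (Section 3.1; A5.2.4 note).
- Death component: a death from confirmed cerebral haemorrhage does not count (Section 3.1).
- Revascularisation component: the clipping counts, because the Primary Endpoints text in Appendix 5 takes its definition from the list that contains it.

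The same illness is therefore excluded under two components and included under a third.

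**2. Possible size of step 1.** The documents give no rate of aneurysm surgery, so only an illustration is possible.
- The plan's own figure first. With a hazard ratio of 0.76 (0.75 × 32% = 24% reduction, Section 10.1), 80% power and two-sided 5%, the Schoenfeld formula gives 4 × (1.960 + 0.842)² / (ln 0.76)² = 31.40 / 0.0753 = 417. This matches the patients-with-events column of Appendix 8, Table 1.
- Split by arm: 417 / 1.76 = 236.9 on placebo and 180.1 on atorvastatin.
- Assume k extra first events that are aneurysm operations unaffected by treatment, divided equally. The ratio becomes (180.1 + k/2) / (236.9 + k/2).
- k = 5 gives 182.6 / 239.4 = 0.763; k = 10 gives 185.1 / 241.9 = 0.765; k = 20 gives 190.1 / 246.9 = 0.770.

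The pull towards 1 is small over this assumed range.

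**3. Where a haemorrhagic stroke is compared between arms.**
- Primary and secondary lists: not counted when confirmed. A stroke without imaging or post-mortem data stays in the A5.2.4 definition, so some unconfirmed bleeds would count.
- Tertiary mortality: a fatal case falls in total mortality and in the vascular, non-coronary group.
- Tertiary hospitalisation: an admitted case falls in a group of other causes that is not defined further.
- Serious adverse events: Section 10.4 plans a Cox model for a first event. Section 9.2 counts planned elective admissions as serious events, so a haemorrhagic stroke after an earlier elective admission would not enter that model.
- Named safety outcomes: none.

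Every case is recorded somewhere, but no comparison is specific to it.

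**4. What a named comparison could deliver.** Assume a rate of 0.05% to 0.2% per year in both arms (not in the documents) over the 27,000 patient-years of Section 10.1.
- Events: 27,000 × 0.0005 = 13.5, up to 27,000 × 0.002 = 54.
- With equal arms, the 95% limits lie at the estimate divided and multiplied by exp(1.96 × 2/√d).
- d = 13.5 gives a factor of 2.91; d = 54 gives 1.70.
- Around an estimate of 1, the interval is 0.34 to 2.91 at the low rate and 0.59 to 1.70 at the high rate.

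The result would be an estimate with a wide interval, not a well-powered test.

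**The case against.** The strongest reply is that nothing is hidden. Cardiovascular events go on the serious adverse event form (Section 9.1), and any death or hospitalisation is a serious adverse event (Section 9.2). An independent committee classifies cardiovascular events and all deaths (Appendix 5). The DMC sees unblinded comparative data (A9.4) and monitors safety continuously (Section 10.7). Total mortality gives some net information. This stands. A reader might infer that an excess on atorvastatin could not be seen, or that no planned analysis would contain it; the documents do not support either reading. The supportable statement is dilution in broad categories.

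A reader might also try to calculate how much of the benefit a rise in haemorrhagic stroke would cancel. The documents give neither a background rate nor a hazard ratio for it, and Section 11.2 recognises only muscle and liver effects. No such offset can be claimed.

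Nor does the aneurysm item hide harm. If bleeds were more frequent on atorvastatin and some were clipped, those operations would count against atorvastatin. The fault is a wrong counting rule, with no built-in direction in favour of the drug.

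Removing haemorrhagic stroke from a composite aimed at atherosclerosis is a legitimate and deliberate choice, and many disease-specific composites are not net of other harms. Tables of adjudicated stroke types could also sit in a statistical analysis plan that is not at hand. That keeps the second part of the point modest. It does not answer the first part, because the primary endpoint definition is fixed in this protocol and contradicts itself.

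**Conclusion.** The point holds in two parts of unequal weight.

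The main part is the inconsistency in the primary endpoint: aneurysm surgery counts while the bleed it may treat is excluded, against an aim limited to atherosclerotic events. This rests on the text alone. Its numerical effect is probably small; the shift from 0.76 to 0.763–0.770 assumes 5 to 20 additional operations unaffected by treatment, a count that the documents do not supply.

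The lesser part is that haemorrhagic stroke has no comparison of its own in the endpoint or safety lists, and the primary hazard ratio is not net of it. The events are captured, adjudicated and available to the DMC, so this is a matter of clear reporting and not evidence that harm would be missed. No size can be put on any excess from the documents.

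**What to change.** 1. Strike the cerebral aneurysm item from the non-cardiac procedure list in Appendix 5, so that it agrees with Section 2.2.2, Section 3.1 and the A5.2.4 exclusions. Make the change while the trial team is blind to outcome by arm, and have the committee reclassify any such operation already accepted. The cost is one line of text and the loss of whatever few events the item would have contributed.

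2. In Section 3.2 and Appendix 6, list adjudicated haemorrhagic stroke (intracerebral and subarachnoid) and stroke of any type, each fatal or non-fatal, as outcomes reported by arm with a hazard ratio and 95% confidence interval, and include them in the DMC reports. A5.2.4 defines intracerebral and cerebellar bleeds but names subarachnoid haemorrhage only as an exclusion, so it needs a short definition. State whether the Bonferroni allowance in Section 3.2 applies to these items; their purpose is estimation.

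The cost of the second change is wording and two table rows, because the events are already collected and classified. The downside is few events and wide intervals.

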### 10.4 Planned analyses

All patients randomised will be included in the analysis, irrespective of whether the study drug is continued (ITT analysis). Cox regression models will be developed for time to occurrence of a first cardiovascular event or serious adverse event using treatment allocation as the independent variable.

The models will be adjusted for factors used in the stratification (centre) and for any baseline imbalances. However, the trial is of sufficient size to expect that most potential confounders (e.g. smoking, aspirin, NSAID/Coxib, corticosteroid, anti-TNF usage etc) are likely to be balanced between the groups. Treatment differences will be expressed as hazard ratios with 95% confidence intervals. Two-sided p values of  $\leq$ 0.05 will be considered significant.

Kaplan-Meier Product Limit (PL) estimates of the survival curves with 95% confidence intervals will be calculated.

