#### Secondary endpoints

Cause-specific mortality (coronary, other vascular and non-vascular death separately)

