#### A5.3 SECONDARY ENDPOINTS

#### A5.3.1 All-cause mortality

Sum of all cardiovascular plus non-cardiovascular deaths.

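### The Bonferroni rule in section 3.2 takes in the statin safety outcomes without exemption, and it is unclear whether it applies to mortality

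*Protocol*

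**What the plan says.** Section 3.2 lists the secondary endpoints of the main trial, introduced as "Components of the primary endpoint separately", with no multiplicity statement under that heading. The tertiary endpoints follow:

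- "Total and cause-specific mortality (coronary, other vascular and non-vascular death separately");
- hospitalisations for other causes;
- "Statin safety-related outcomes (persistent elevation of ALT or AST; myopathy", the latter defined by muscle symptoms with CK above ten times the upper limit of normal);
- lipid differences in a random sample;
- HAQ and EQ5D.

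The list ends: "Allowance for multiple hypothesis testing in these analyses will be made using the" Bonferroni correction. No outcome is exempted and no number of tests is given.

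Three other places bear on this:

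- Section 10.4 plans Cox models for a first cardiovascular event or a serious adverse event, with hazard ratios and 95% confidence intervals. "Two-sided p values of" at most 0.05 count as significant, and no correction is mentioned.
- Appendix 1 (A1.5) analyses safety outcomes in the disease activity sub-study by logistic regression at the same two-sided 0.05, again with no correction.
- Appendix 5 puts "Cause-specific mortality (coronary, other vascular and non-vascular death separately") under its secondary endpoints. Its section A5.3, also headed secondary endpoints, defines all-cause mortality as "Sum of all cardiovascular plus non-cardiovascular deaths".

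**The concern.** Bonferroni limits false positive claims. For benefit that is the error to guard against. For harm the costlier error is usually the opposite one: a true excess reported as non-significant. A correction on safety comparisons makes that error more likely.

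It matters in this trial. Section 2.2.1 gives unproven safety in RA patients as one reason for running it. Section 11.2 names myopathy and liver function abnormalities as the only two recognised adverse effects of atorvastatin, and these are the two outcomes placed under the correction. Section 9.3 limits the recording of other adverse events on the CRF to those that lead to discontinuation of study treatment, so there are few other safety comparisons to fall back on.

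The rule also sits badly with the rest of the protocol. A safety comparison in the 326-patient sub-study is judged at 0.05, while liver and muscle toxicity in a trial of about 5,342 patients is judged at a stricter level that the text does not allow one to calculate. For mortality, the tier decides whether the correction applies, and the protocol gives two tiers.

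**Working it through.** **Conventions.** The plan gives no figure for the corrected tests, so the check starts with the convention behind its own events table. For a 24% reduction, Appendix 8 Table 1 gives 417 patients with events. Schoenfeld's formula with equal arms, two-sided 5% and 80% power gives

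4 × (1.960 + 0.842)² / (ln 0.76)² = 31.40 / 0.0753 = 417.

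The plan's figure is reproduced, so two-sided 5% and 1:1 allocation are reasonable inputs below.

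**Number of tests, k.**

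- By item: mortality, hospitalisations, statin safety, lipids, functional outcome. k = 5, and the level per test is 0.05/5 = 0.01 (z = 2.576).
- Singly: 4 mortality outcomes, at least 1 hospitalisation outcome, ALT/AST, myopathy, at least 1 lipid, HAQ, EQ5D. k is at least 10, and the level is 0.05/10 = 0.005 (z = 2.807).

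The hospitalisation item is open-ended, so k has no upper limit from the text.

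**Loss for any comparison.** If power at two-sided 0.05 is 1 − β, then power after correction is Φ(1.960 + z(1−β) − z(corrected)).

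- 80% becomes Φ(1.960 + 0.842 − 2.576) = 59% at k = 5, and Φ(1.960 + 0.842 − 2.807) = 50% at k = 10.
- 90% becomes 75% and 67%.

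**Illustration on event rates.** Section 10.1 gives 5,342 patients, so n = 5,342/2 = 2,671 per arm. The event rates are assumptions; the protocol gives none by arm. The formula is

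power = Φ((|p1 − p0| − z·s0)/s1),

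where s0 = √(2p̄(1 − p̄)/n), p̄ is the mean of p0 and p1, and s1 = √(p0(1 − p0)/n + p1(1 − p1)/n).

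For 0.5% v 1.2%, s0 = s1 = 0.00251, and the argument of Φ is 0.83, 0.21 and −0.02 at k = 1, 5 and 10. For 1% v 2%, s0 = 0.00333 and s1 = 0.00332, and the argument is 1.05, 0.43 and 0.20.

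| Assumed rates | Uncorrected | k = 5 | k = 10 | Relative loss |
|---|---|---|---|---|
| 0.5% v 1.2% | 80% | 58% | 49% | 27% to 38% |
| 1% v 2% | 85% | 67% | 58% | 22% to 32% |
| 0.5% v 1.0% | 56% | 32% | 25% | 43% to 56% |
| 0.1% v 0.2% | 15% | 5% | 3% | little power at any level |

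The last row is relevant to myopathy, which the table in Appendix 7 grades as uncommon, that is between 0.1% and 1%. At the bottom of that range the test is weak with or without the correction.

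**Mortality.** This part needs no arithmetic. Section 3.2 lists total and cause-specific death among the tertiary endpoints, above the Bonferroni sentence. Appendix 5 lists both as secondary. Both statements are current text, and they disagree on the tier.

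**The case against.** The strongest reply is that patients are not protected by a p value. The independent DMC monitors these outcomes, has access to unblinded comparative data and works under no formal stopping rule. Sections 6.2.3 and 11.2 and Appendix 6 act on each patient's ALT/AST and CK. This stands: the effect is confined to what the final report calls significant. It does not answer the point, because the final report is where the safety conclusion is drawn.

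A second reply concerns scope. The sentence ends the main-trial list in a section that covers secondary and tertiary endpoints, so *these analyses* might include both tiers. That is possible, and the safety problem is the same on either reading. A reader might infer that the secondary components are wrongly left uncorrected. The documents do not support that: the scope is uncertain, and leaving supportive components of the primary endpoint uncorrected is not an error.

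Three further inferences go too far:

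- *The rule halves the chance of declaring a harm.* On the two main illustrations the relative loss is roughly 20% to 40%. It passes one half only at k = 10 for a small excess that the trial would detect barely more often than not even without correction.
- *Confidence intervals become wider.* The sentence concerns hypothesis tests. No section adjusts an interval, and section 10.4 specifies 95% intervals for its Cox models.
- *Mortality has two significance levels.* Appendix 5 defines endpoints and states no level. The documents show a conflict of tier, which leaves the application of the correction unclear and no more than that.

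**Conclusion.** The point holds, as a fault in a rule the protocol states. Persistent ALT/AST elevation and myopathy fall under a Bonferroni correction with no exemption, while serious adverse events and sub-study safety outcomes are judged at an uncorrected two-sided 0.05. A harm that the trial could detect with 80% power at 0.05 would have 59% if the list counts as 5 tests and 50% if it counts as 10. On the two main sets of assumed rates the relative loss of power is roughly 20% to 40%.

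These sizes rest on assumed event rates, 1:1 allocation of 5,342 patients, and a count of tests that the protocol does not fix. The direction of the effect depends on none of them. The mortality conflict is separate and rests on the text alone. The whole point is worth correcting, but it concerns reporting and wording; the conduct of the trial is not in question.

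**What to change.** 1. In section 3.2, exempt the statin safety outcomes from the Bonferroni correction and report each with an unadjusted 95% confidence interval and p value, in line with section 10.4 and A1.5.
2. State whether the correction covers the tertiary efficacy endpoints only or the secondary endpoints as well, and give the number of tests in the family.
3. Put all-cause and cause-specific mortality in the same tier in section 3.2 and Appendix 5, so that it is settled before the analysis whether they are corrected.

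The cost is wording in two places. No data, visits or sample size change. The downside is a somewhat higher chance of a false safety signal, which is the more acceptable error for outcomes of this kind.
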